3.11 Clinical management of the 'early' tracheostomy arm

Patients allocated to this arm will have either a percutaneous or surgical tracheostomy at any time during day 1 to day 4 following ICU admission. The technique for tracheostomy will be determined by local practice and will be recorded. Immediate adverse events will be recorded.

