3.12 Clinical management of the 'late' tracheostomy arm

Patients allocated to this arm should not have a tracheostomy before day 10 following ICU admission.

The clinician responsible for their care will review their need for a tracheostomy at day 10, when either of the following strategies may be followed:

- (a) a percutaneous or surgical tracheostomy is performed on or after day 10

or

- (b) no tracheostomy is carried out as it is no longer appropriate to do so (or the patient is no longer in ICU).

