3.22 Type of analysis

The principal comparisons will be between those allocated to “early” tracheostomy and those allocated to “late” tracheostomy (the “intention to treat” principle). The primary outcome variable will be proportion of patients surviving to 30 days post randomisation in each arm which will be compared using Fisher’s exact test.

Hospital and ICU mortality will also be compared between arms using Fisher’s exact test. The survival curves for the two arms will be calculated using the Kaplan-Meier method, with the starting time being the time of randomisation, and compared using a log-rank test. Differences in length of ICU stay, hospital stay, number of days sedated and number of antibiotic-free days between arms will be tested using the Wilcoxon rank-sum test.

Mr [name], Senior Statistician at ICNARC, will act as trial statistician and perform the analyses.

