3.23 Subgroup and exploratory analyses

Additional analyses will explore:

- The effect of early tracheostomy on length of hospital stay, 30 day and hospital mortality in subgroups with different severity of illness determined by APACHE II scoring on ICU admission
- The effect of early tracheostomy on length of hospital stay, 30 day and hospital mortality in broad subgroups (intracranial pathology, respiratory infections etc.) with different causes of respiratory failure
- The effect of early tracheostomy on length of hospital stay, 30 day and hospital mortality in subgroups with different tracheostomy procedures (percutaneous or surgical), assuming sufficient patients in the “late” arm have a tracheostomy to allow this analysis.
- The effect of early tracheostomy on length of hospital stay, 30 day and hospital mortality in subgroups defined by the grade of the primary operator, assuming sufficient patients in the “late” arm have a tracheostomy to allow this analysis.
- The effect of early tracheostomy on length of hospital stay, 30 day and hospital mortality in subgroups of ICUs of varying sizes.
- Whether the duration of ventilatory support can be predicted using a model based on clinical and laboratory information available on days 1-4, and whether the subsequent use of tracheostomy adds explanatory power to the model.

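### Two exploratory subgroups in 3.23 (technique used, operator grade) exist only for patients who had a tracheostomy, so the early-versus-late effect within them is biased by selection even if timing does nothing

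*Protocol*

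**What the plan says.** Section 3.23 lists six additional analyses. Two of them estimate the effect of early tracheostomy on length of hospital stay, 30-day mortality and hospital mortality: one "in subgroups with different tracheostomy procedures (percutaneous or surgical"), the other "in subgroups defined by the grade of the primary operator". Each has a single proviso, that sufficient late-arm patients "have a tracheostomy to allow this analysis".

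Membership of these subgroups depends on the management sections:

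- Section 3.11: early-arm patients have the procedure "at any time during day 1 to day 4 following ICU admission".
- Section 3.12: "Patients allocated to this arm should not have a tracheostomy before day 10 following ICU admission". At the day-10 review, one permitted course is that "no tracheostomy is carried out as it is no longer appropriate to do so (or the patient is no longer in ICU").
- Section 3.3 expects a number of late-arm patients not to need a tracheostomy on day 10.
- Section 3.4 counts the primary outcome from randomisation.
- Section 3.22 applies intention to treat to the main analysis: "The principal comparisons will be between those allocated to" early and those allocated to late tracheostomy.

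**The concern.** A subgroup analysis of a randomised comparison is sound when membership is settled before allocation, or at least cannot be affected by it. Neither holds here. Technique and operator grade have no value for a patient who never had a tracheostomy, and allocation strongly affects who has one. The proviso on late-arm numbers confirms that late-arm patients without the procedure are outside the comparison.

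Two selections then act on the late arm and hardly at all on the early arm. Patients who die before day 10 are lost, which lowers late-arm mortality. Patients who recover before day 10 are also lost, which leaves the sicker ones and raises it. Late-arm members must also have stayed at least to day 10, which lengthens their stay.

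The estimate can therefore move away from no effect when timing has none. The proviso guards only against small numbers, and a larger biased comparison is merely a more precise one. What is at stake is the credibility of any statement that the benefit or harm of early tracheostomy differs by technique or operator. The other subgroups in 3.23 (APACHE II on admission, cause of respiratory failure, ICU size) can be defined for every randomised patient and do not share the fault.

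**Working it through.** The protocol gives no figure for these subgroups, so there is none to reproduce. The calculation below shows how far the contrast can move under no effect.

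**Who enters the subgroups**

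| Course after randomisation | Early arm | Late arm, compliant |
|---|---|---|
| Dies before day 10 | In, if the procedure was done by day 4 | Out |
| Recovers or leaves ICU before day 10 | In, if the procedure was done by day 4 | Out |
| In ICU at day 10, procedure judged needed | In | In |
| In ICU at day 10, procedure judged not needed | In | Out |

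**Inputs**

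- Mortality m = 0.30 in both arms. This is the late-arm figure in 3.20, where hospital mortality stands in for 30-day mortality.
- True relative risk 1.00; all early-arm patients enter the subgroup.
- f, the share of 30-day deaths falling before day 10 of ICU stay. Not in the documents; assumed 0.2 to 0.5.
- k, the risk of tracheostomised late-arm patients relative to other day-10 survivors. Not in the documents; assumed 1.5 to 2, with half of the survivors tracheostomised.

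**Step 1: lose early late-arm deaths only.** Risk among late-arm day-10 survivors is r = m(1 − f)/(1 − mf). The apparent early/late relative risk is m/r.

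**Step 2: add selection on need.** If half have k times the risk of the rest, the tracheostomised half has risk 2kr/(k + 1). That is 1.20r for k = 1.5 and 1.333r for k = 2, so the Step 1 ratio is divided by 1.20 or 1.333.

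| f | r | Step 1 RR | Step 2 RR, k = 1.5 | Step 2 RR, k = 2 |
|---|---|---|---|---|
| 0.2 | 0.24/0.94 = 0.255 | 1.18 | 0.98 | 0.88 |
| 0.3 | 0.21/0.91 = 0.231 | 1.30 | 1.08 | 0.98 |
| 0.4 | 0.18/0.88 = 0.205 | 1.47 | 1.22 | 1.10 |
| 0.5 | 0.15/0.85 = 0.176 | 1.70 | 1.42 | 1.28 |

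**Step 3: a second form of the same check.** Let s be the share of 30-day survivors in the late arm who never need the procedure, and let every later death be tracheostomised. Late subgroup mortality is 0.30(1 − f)/[0.30(1 − f) + 0.70(1 − s)]. With s = 0 this is Step 1. With s between 0.25 and 0.5 the relative risk runs from 0.74 (f = 0.2, s = 0.5: 0.24/0.59 = 0.407) to 1.35 (f = 0.5, s = 0.25: 0.15/0.675 = 0.222). Both forms span 1.

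**Step 4: hospital stay.** No rate is needed for the direction. A compliant late-arm member cannot have died or left before day 10; an early-arm member can. The early-arm stay is pulled down relative to the late-arm stay.

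**Step 5: does the proviso help?** Sample size appears in none of these formulas, so more late-arm procedures leave the bias where it is.

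**The case against.** The strongest reply is that these are two of six analyses labelled exploratory and conditional on numbers, and that the trial's conclusion does not rest on them. That is right, and it limits the weight of the point. It does not remove it: an exploratory label warns of multiplicity and low power, not of an estimate that departs from the null by construction. Nor is this detail left to an analysis plan, because the protocol itself names the subgroup variable, the outcomes and the condition.

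A reader might infer that 3.23 contradicts 3.22. It does not. Section 3.22 applies intention to treat to the principal comparisons, and these analyses are additional.

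A reader might also infer that mortality will be biased against early tracheostomy, or that a particular false-positive rate follows. The documents support neither. Once selection on need is allowed for, the relative risk can fall on either side of 1 or close to it. A rejection rate would depend on the subgroup sizes and on how ventilation time relates to death, and the protocol gives neither.

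Three further qualifications stand:

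- The exclusion of late-arm patients is not total. Section 3.20 expects about 2% crossover in the late arm.
- Some early-arm patients will die or recover before their procedure and leave the subgroup too.
- Technique follows local practice (3.11, 3.13), so the main problem is selection into having a procedure at all, rather than choice of technique after allocation.

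**Conclusion.** The point holds for the technique and operator-grade bullets of 3.23. Within them, early-arm patients are compared with a late-arm group selected on survival, ICU stay and need at day 10.

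- **Hospital stay:** the bias makes early tracheostomy look shorter. This direction follows from the protocol's own timing rules.
- **Mortality:** the direction is unknown. Under no effect and 30% mortality, the spurious relative risk is 1.18-1.70 from losing early deaths alone and about 0.88-1.42 with need-based selection added. These ranges rest on the assumed share of deaths before day 10, the assumed risk ratio and the assumed half of survivors tracheostomised. They illustrate the bias and do not predict its size.

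The primary intention-to-treat comparison is unaffected. The change is worth making, but the trial's main result does not depend on it.

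**What to change.** In 3.23, delete the early-versus-late estimates of mortality and length of stay from these two bullets. Report the technique used and the operator's grade descriptively among patients who had the procedure, for example alongside procedural complications.

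If a technique subgroup is still wanted, define it by the recruiting ICU's usual technique, classified without reference to allocation or outcome. Include all randomised patients as allocated and test the treatment-by-subgroup interaction. The same substitute is less secure for operator grade, since a usual grade may not be a stable feature of a unit.

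The cost is a wording change and no extra patients. The optional technique subgroup adds one classification per ICU, which would be retrospective for units already open. Its downside is that a unit-level variable is coarser than the procedure each patient had and may be confounded with other features of the unit, such as size or case mix.

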3.24 Compliance and crossovers

The primary responsibility for the care of ventilated patients on ICUs passes from one consultant to the next on a daily or weekly basis depending on the type of duty roster. To ensure compliance with the trial protocol throughout a patient’s stay, and to avoid cross-over after allocation to either the “early” or “late” arm, only ICUs where *all* the consultants agree to abide by the protocol will be used as recruiting centres.

3.25 Frequency and timing of analyses

The frequency and timing of analyses will be determined by the Data Monitoring and Ethics Committee (DMEC) in line with its Standard Operating Procedures (see page 23).

3.26 Economic analysis

Currently there is no funding available for an economic analysis. The steering group will investigate strategies to fund an economic analysis.

3.27 Will there be NHS cost implications as a result of this trial?

The patient will not require any special tests or extra hospital visits over and above standard care.

Materials required for data collection will be supplied by the TracMan Trial Office. The data collection burden will be kept to the minimum compatible with a scientifically valid result from the trial. The main NHS cost will be an opportunity cost incurred by in-post personnel seeking consent and collecting the data, which we expect to amount to 1-2 hours/patient.

3.28 Ethics approval

New standard operating procedures for Research Ethics Committees (RECs) came into force from 1st March 2004, more details are available from <http://www.corec.org.uk/PDF/Guidance%20for%20Applicants%20to%20RECs.pdf>.

Under these new rules the ethics application made by the Chief Investigator ([name]), once approved, will cover all collaborating sites. However, whilst this is the only ethical review of the trial required as part of the new procedures, it is necessary for collaborating Sites to have a Site Specific Assessment (SSA) carried out locally before the trial can begin in their hospital(s).

Under the new rules a “Sponsor” is required for the trial. The Oxford Radcliffe Hospitals NHS Trust will assume this role.

3.28.1 Site Specific Assessments

The Principal Investigator at each Trust will be notified by the Trial Office when it is time to apply for a Site Specific Assessment (SSA). A SSA is not an *ethical* review, but a process of confirming that there are no objections to the trial on site-specific grounds. Further details will be forthcoming from the Trial Office at the appropriate time, as the details of the new system become clearer.

3.29 The EU Directive for Clinical Trials of Medicines in Human Subjects

The EU Clinical Trials Directive (Directive 2001/20/EC) (<http://www.ncchta.org/eudirective/index.asp>), came into force on 1st May 2004. As this trial does **not** involve a “medicinal product” it is not required to comply with the Directive.

This trial will be managed according to the Medical Research Council’s Guidelines for Good Clinical Practice in Clinical Trials (<http://www.mrc.ac.uk/pdf-ctg.pdf>).

3.30 Trial funding

The Intensive Care Society funded the trial 2004 to end March 2006. The Medical Research Council funded the trial from 1st April 2006. Funding covers the trial office staff who facilitate the trial. There is no direct financial support for collaborating ICUs. Many Trusts have a Research and Development office that may be able to help locate funding.

3.31 Publication of results

The success of the trial depends on the collaboration of consultants from across the UK. Equal credit will be given to those who have wholeheartedly collaborated in the trial.

The results of the trial will be reported first to trial collaborators. The main report will be drafted by the trial office team, and the final version will be agreed by the Steering Committee before submission for publication, on behalf of the collaboration.

Due to limited resources, it will be not be possible to provide each surviving patient with a personal copy of the results of the trial. Instead, with due regard to copyright issues relating to the publication of the results in peer reviewed journals, the trial results will be published on the ICS web site (<http://www.ics.ac.uk/>), where any member of the public may view the results. The ICS web site address will be provided on the patient information sheet.

3.32 Recruitment of ICUs

Identification of potential collaborators is currently ongoing. We always welcome new collaborators, if you are interested please contact [name] in the Trial Office on [name].

3.33 The Steering Committee

The trial is guided by a group of respected and experienced critical care personnel and trialists as well as a 'lay' representative. Face to face meetings will be held at regular intervals determined by need but not less than once a year. Routine business is conducted by email and post. Current membership of the Steering Committee is listed in Appendix 10.

3.33.1 Standard Operating Procedures for the Steering Committee:

The Steering Committee, in the development of this protocol and throughout the trial will take responsibility for:

- Major decisions such as a need to change the protocol for any reason
- Monitoring and supervising the progress of the trial
- Reviewing relevant information from other sources
- Considering recommendations from the DMEC
- Informing and advising on all aspects of the trial.

3.34 The Data Monitoring and Ethics Committee (DMEC)

3.34.1 Standard Operating Procedures for the DMEC:

- 1) During the period of recruitment into the study, interim analyses of the proportion of patients alive at 30 days and analyses of deaths from all causes at 30 days will be supplied, in strict confidence, to the chairman of the DMEC, along with any other analyses that the committee may request.
- 2) In the light of these analyses, the DMEC will advise the Chairman of the Steering Committee if, in their view, the randomised comparisons have provided both (i) 'proof beyond reasonable doubt' that for all, or some, the treatment is clearly indicated or clearly contra-indicated and (ii) evidence that might reasonably be expected to materially influence future patient management.

- 3) Appropriate criteria of proof beyond reasonable doubt cannot be specified precisely, but the DMEC will work on the principle that a difference of at least 3 standard deviations in an interim analysis of a major outcome event may be needed to justify halting, or modifying, a study before the planned completed recruitment. These criteria have the practical advantage that the exact number of interim analyses would be of little importance, and so no fixed schedule is proposed.
- 4) Following a report from the DMEC, the Steering Committee will decide whether to modify entry to the study (or seek extra data). Unless this happens the Steering Committee and the collaborators will remain ignorant of the interim results.
- 5) Data relating to the safety of patients will be reviewed by the Chair of the DMEC once 50 patients have been randomised to the trial. The data reviewed will specifically relate to:
 - a) procedure related 'serious, unanticipated adverse events' (death or serious disability)
 - b) procedure related adverse events/ complications
 - c) deaths at 30 days (any cause)
- 6) The DMEC will meet to review one year (Aug 05), or at 100 deaths, whichever occurs first. The DMEC will meet annually thereafter.

The DMEC comprises of a senior statistician, a senior clinician, and a senior trialist (Chair), see Appendix 11.

Method of randomisation	Randomly generated assignment contained in sequentially numbered envelopes	Randomly generated assignment contained in sequentially numbered envelopes	Randomly generated assignment contained in envelopes. Stratified into three groups (trauma and GCS <= 8, trauma and GCS > 8, respiratory failure) Re-randomisation at day 10-14 if in the late group	Assignment by date, odd days = "early" arm, even days = "late" arm	Assignment determined by the last digit of the patient's hospital number	Assignment determined by the last digit of the patient's hospital number	Sequentially divided into 2 arms
Early arm definition	Tracheostomy within 2 days of start of artificial ventilation	Tracheostomy placement during next available operating day (usually day 3)	Tracheostomy between day 3 and 5 after admission	Tracheostomy within 7 days of admission	Tracheostomy 3-4 days after initiation of ventilation	Tracheostomy 2 days after initiation of ventilation	Tracheostomy after day 3 of mechanical ventilation
Late arm definition	Tracheostomy >=14 days after initiation of artificial ventilation if still ventilated	Tracheostomy on post burns day 14 if still intubated	Tracheostomy on day 10-14 post admission if still intubated and major head injury. At which point possible to re-randomised to either (1) tracheostomy on day 10-14 or (2) tracheostomy later than day 21	Tracheostomy at least 8 days after admission	Tracheostomy >14 days after initiation of ventilation	Tracheostomy up to 21 days after initiation of ventilation	Tracheostomy >10 days after initiation of ventilation

Literature search – Tracheostomy clinical trials – Appendix 1 continued/...

Authors	Rumbak et al ¹¹	Saffle et al ¹²	Sugerman et al ¹⁷	Rodriguez et al ¹⁸	Dunham et al ³²	Stauffer et al ³³	El-Nagger et al ³⁴
Tracheostomy technique	Percutaneous	Surgical or percutaneous (in operating theatre)	Physician's choice, (73% percutaneous)	Not stated	Surgical	Not stated	Not stated
Early/late n	60/60	21/23	53/59	51/55	34/40	Not stated	26/26
ICU mortality early arm	Not stated	Not stated	Not stated	Not stated	Not stated	Not stated	Not stated
ICU mortality late arm	Not stated	Not stated	Not stated	Not stated	Not stated	Not stated	Not stated
Hospital mortality early arm	19 (32%)*	4 (19%)	13 (25%)	9* (18%)	Not stated	Not stated	Not stated
Hospital mortality late arm	37 (62%)*	6 (26%)	11 (19%)	13* (23%)	Not stated	Not stated	Not stated
ICU LOS early arm (days)	Mean 4.8 SD 1.4	Not stated	Mean 20 SD 2	Mean 16 SD 1	Not stated	Not stated	Not stated
ICU LOS late arm (days)	Mean 16.2 SD 3.8	Not stated	Mean 24 SD 2	Mean 37 SD 4	Not stated	Not stated	Not stated
Hospital LOS early arm (days)	Not stated	Mean 58.4 SD 6.3 Range 14-124	Not stated	Mean 34 SD 4	Not stated	Not stated	Not stated
Hospital LOS late arm (days)	Not stated	Mean 57.3 SD 8.0 Range 11-153	Not stated	Mean 51 SD 4	Not stated	Not stated	Not stated
Patients developing pneumonia, early arm	3 (5%)	21 (100%)	26 (49%)	25* (50%)	20 (59%)	Not stated	Not stated
Patients developing pneumonia, late arm	15 (25%)	22 (96%)	32 (57%)	47* (85%)	20 (50%)	Not stated	Not stated
Late arm patients receiving tracheostomy	Not stated	Not stated	Not stated	Not stated	20 (50%)	Not stated	10 (19%)
Other outcomes	Laryngeal trauma equal in arms	1/21 (4.8%) decannulated by 14 days in early arm, 7/23 (30%) decannulated by 14 days in late arm	None stated	None stated	None stated	None stated	None stated
Comments	* = 30 day mortality	Mortality assumed to be hospital mortality	Additional group recruited on day 10-14 post injury, not included in this summary. Mortality assumed to be hospital mortality.	* = Calculated values not reported in the original publication	* = Text is ambiguous, elsewhere ventilated > 7 days is given as an inclusion criterion.	No data on outcome by group in paper	No data on outcome by group in paper

Literature search: Tracheostomy retrospective chart reviews/prospective observational studies

APPENDIX 2

Authors	Teoh et al ¹⁹	Brook et al ²⁰	Armstrong et al ²⁴	Blot et al ²¹	D'Amelio et al ²²	Lesnik et al ²³
Publication year	2001	2000	1998	1995	1994	1992
Patient population	30 neurosurgical patients	90 patients in medical ICU	157 blunt trauma patients	53 neutropaenic patients	31 head injured patients	101 blunt trauma patients
Setting	Single neurosurgical unit, Singapore	Single medical ICU, USA	Single hospital, USA	Single ICU, France	Single neurosurgical unit, USA	Single hospital, USA
Age limits	Not stated	>17 years	Not stated	Not stated	Not stated	Not stated
Exclusions	Percutaneous tracheostomy	Transfers from other ICUs	Patients with craniofacial injuries	Not stated	Open gastrostomy*	Patients with craniofacial injuries
Early group definition	Tracheostomy before or on day 7	Tracheostomy before or on day 10 of mechanical ventilation	Tracheostomy before or on day 6 of mechanical ventilation	Tracheostomy before or on day 2	Tracheostomy before or on day 7	Tracheostomy before or on day 4
Late group definition	Tracheostomy after day 7	Tracheostomy after day 10	Tracheostomy after day 6	Tracheostomy after day 2	Tracheostomy after day 7	Tracheostomy after day 4
Tracheostomy technique	Surgical	Not stated	Not stated	Surgical	Percutaneous and surgical	Surgical (implied not stated)
Early/late n	12/18	53/37	62/95	20/33	21/10	32/69
ICU mortality early group	Not stated	Not stated	Not stated	14 (70%)	Not stated	Not stated
ICU mortality late group	Not stated	Not stated	Not stated	26 (79%)	Not stated	Not stated
Hospital mortality early group	Not stated	15 (28%)	7 (11.3%)	15 (75%)	2 (10%)	Not stated
Hospital mortality late group	Not stated	14 (37.8%)	11 (11.6%)	27 (82%)	1 (10%)	Not stated
ICU LOS early group (days)	Not stated	Mean 15.6 SD 9.3	Mean 15 SD 12	Mean 28 SD 24	Mean 12.6 SD not stated	Not stated
ICU LOS late group (days)	Not stated	Mean 29.3 SD 15.4	Mean 29 SD 26	Mean 19 SD 18	Mean 26.2 SD not stated	Not stated
Hospital LOS early group (days)	Not stated	Mean 44.8 SD 30.3	Mean 33 SD 24	Mean 31 SD 26	Not stated	Not stated
Hospital LOS late group (days)	Not stated	Mean 49.6 SD 22.3	Mean 68 SD 48	Mean 23 SD 21	Not stated	Not stated
Patients developing pneumonia, early group	Not stated	16 (30%)	Not stated	2 (10%)	Not stated	6 (19%)
Patients developing pneumonia, late group	Not stated	16 (43.2%)	Not stated	3 (9%)	Not stated	41 (59%)
Comments					* = All patients also had a percutaneous gastrostomy	

Literature search: Data to inform the protocol development and power calculations

APPENDIX 3

Section 1 of table

Reference number	Study type	Study topic	Year of publication	First author surname	Country	n Tracheostomy patients	Patient group
³⁵	Prospective case series	Single dilator technique	2003	Westphal	Germany	10	Long term ventilation patients
³⁶	Prospective case series	Complications of tracheostomy in ICU	2003	Francois	France	118	Mixed medical/surgical ICU patients
³⁷	Prospective case series	PDT	2003	Polderman	Netherlands	211	Mixed medical/surgical ICU patients
³⁸	Prospective case series	Nosocomial pneumonia in ICU patients with PDT	2003	Rello	Spain	110	Mixed medical/surgical ICU patients
